12.4 List of Excluded Concomitant Medications

These lists are not inclusive of all possible prohibited medications. In case of doubt, the Investigator must contact the local medical monitor.

- Use of hormonal medications such as hormone therapy, HRT or hormonal contraception or any treatment for menopausal symptoms (prescription, over the counter or herbal) is not allowed during the study.
- Investigational research products that have not been approved for any indication in the country where the subject is enrolled.

Strong CYP1A2 Inhibitors (AUCr > 5)	
Inhibitor	Therapeutic Class
Angelica root - Bai Zhi (Angelica dahurica radix)	Herbal Medications
ciprofloxacin	Antibiotics
clinafloxacin	Antibiotics
enoxacin	Antibiotics
fluvoxamine	SSRIs
oltipraz	Cancer Chemopreventive Agents
rofecoxib	NSAIDS
zafirlukast	Antiasthmatics
Moderate CYP1A2 Inhibitors (AUCr ≥ 2 and AUCr ≤ 5)	
Inhibitor	Therapeutic Class
3,4-methylene-dioxymethamphetamine (MDMA)	Recreational Drugs
etintidine	H-2 Receptor Antagonists
genistein	Food Products
idrocilamide	Muscle Relaxants
methoxsalen (8-methoxypsoralen)	Antipsoriatics
mexiletine	Antiarrhythmics
osilodrostat	Adrenal Steroidogenesis Inhibitors
oral contraceptives	Oral Contraceptives
phenylpropanolamine	Vasoconstrictors
pipemidic acid	Antibiotics
propafenone	Antiarrhythmics
propranolol	Alpha/Beta Adrenergic Antagonists
troleandomycin	Antibiotics
vemurafenib	Kinase Inhibitors

AUCr: area under the concentration-time curve ratio; CYP: cytochrome P450; MDMA: 3,4-methylene-dioxymethamphetamine; NSAID: nonsteroidal anti-inflammatory drugs; SSRI: Selective serotonin reuptake inhibitors.

Estrogen-Only Medicines	
Brand Name	Generic Name
Alora	Estradiol
Cenestin	Synthetic Conjugated Estrogens
Climara	Estradiol
Delestrogen	Estradiol Valerate
Divigel	Estradiol
Elestrin	Estradiol
Enjuvia	Synthetic Conjugated Estrogens
Esclim	Estradiol
Estrace	Estradiol
Estraderm	Estradiol
Estrasorb	Estradiol
Estring	Estradiol
EstroGel	Estradiol
Evamist	Estradiol
Femring	Estradiol Acetate
Femtrace	Estradiol Acetate
Menest	Esterified Estrogen
Menostar	Estradiol
(only used to prevent osteoporosis)	
Minivelle	Estradiol
Ogen	Estropipate
Ortho-Est	Estropipate
Premarin	Conjugated Estrogens
Vagifem	Estradiol
Vivelle	Estradiol
Vivelle-Dot	Estradiol
Progestin-Only Medicines	
Brand Name	Generic Name
Prometrium	Micronized Progesterone
Aygestin	norethindrone acetate
Provera	Medroxyprogesterone Acetate

Estrogen-Only Medicines	
Combination Estrogen and Progestin Medicines	
Brand Name	Generic Name
Activella	Estradiol/
	Norethindrone Acetate
Angeliq	Estradiol/ Drospirenone
Climara Pro	Estradiol/
	Levonorgestrel
Combipatch	Estradiol/
	Norethindrone Acetate
Jinteli	Ethinyl Estradiol/
	Norethindrone Acetate
Mimvey	Estradiol/
	Norethindrone Acetate
Femhrt	Norethindrone Acetate/
	Ethinyl Estradiol
Prefest	Estradiol/
	Norgestimate
Prempro	Conjugated Estrogen/
	Medroxyprogesterone
Premphase	Conjugated Estrogen/
	Medroxyprogesterone
Combination Estrogen and Hormone Medicines	
Brand Name	Generic Name
Duavee	Conjugated Estrogen/ Bazedoxifene

12.5 Liver Safety Monitoring and Assessment

Any subject enrolled in a clinical study with active drug therapy and reveals an increase of serum aminotransferases (AT) to $> 3 \times \text{ULN}$ or bilirubin $> 2 \times \text{ULN}$ should undergo detailed testing for liver enzymes (including at least ALT, AST, ALP and TBL). Testing should be repeated within 72 hours of notification of the test results. For studies for which a central laboratory is used, alerts will be generated by the central laboratory regarding moderate and severe liver abnormality to inform the investigator and study team. Subjects should be asked if they have any symptoms suggestive of hepatobiliary dysfunction.

Definition of Liver Abnormalities

Confirmed abnormalities will be characterized as moderate and severe where ULN:

	ALT or AST		TBL
Moderate	$> 3 \times \text{ULN}$	or	$> 2 \times \text{ULN}$
Severe	$> 3 \times \text{ULN}$	and	$> 2 \times \text{ULN}$

In addition, the subject should be considered to have severe hepatic abnormalities for any of the following:

- ALT or AST $> 8 \times \text{ULN}$;
- ALT or AST $> 5 \times \text{ULN}$ for more than 2 weeks;
- ALT or AST $> 3 \times \text{ULN}$ **AND** TBL $> 2 \times \text{ULN}$ or INR > 1.5 ; or
- ALT or AST $> 3 \times \text{ULN}$ with the appearance of fatigue, nausea, vomiting, right upper quadrant pain or tenderness, fever, rash and/or eosinophilia ($> 5\%$ increase above baseline).

The investigator may determine that abnormal liver test results, other than as described above, may qualify as moderate or severe abnormalities and require additional monitoring and follow-up.

Follow-up Procedures

Confirmed moderate and severe abnormalities in hepatic tests should be thoroughly characterized by obtaining appropriate expert consultations, detailed pertinent history, physical examination and laboratory tests. The site staff is to complete the liver abnormality case report form (LA-CRF). Subjects with confirmed liver aminotransferases (ALT or AST) should be followed as described below.

Confirmed moderately abnormal liver tests should be repeated 2 to 3 times weekly then weekly or less if abnormalities stabilize or the study drug has been discontinued and the subject is asymptomatic.

Severe liver test abnormalities as defined above, in the absence of another etiology, are considered an important medical event and should be reported as a SAE. The sponsor should be contacted and informed immediately of all subjects for whom severe hepatic liver function abnormalities possibly attributable to study drug are observed.

To further assess abnormal hepatic laboratory findings, the investigator is expected to:

- Obtain a more detailed history of symptoms and prior or concurrent diseases. Symptoms and new-onset diseases is to be recorded as “AEs” within the eCRF. Illnesses and conditions such as hypotensive events, and decompensated cardiac disease that may lead to secondary liver abnormalities should be noted. Nonalcoholic steatohepatitis is seen in obese hyperlipoproteinemic and/or diabetic patients, and may be associated with fluctuating AT levels. The investigator should ensure that the medical history form captures any illness that predates study enrollment that may be relevant in assessing hepatic function.
- Obtain a history of concomitant drug use (including nonprescription medication, complementary and alternative medications), alcohol use, recreational drug use and special diets. Medications, is to be entered in the eCRF. Information on alcohol, other substance use and diet should be entered on the LA-CRF or an appropriate document.
- Obtain a history of exposure to environmental chemical agents.
- Based on the subject’s history, other testing may be appropriate including:
 - Acute viral hepatitis (A, B, C, D, E or other infectious agents),
 - Ultrasound or other imaging to assess biliary tract disease,
 - Other laboratory tests including INR and DBL.
- Consider gastroenterology or hepatology consultations.
- Submit results for any additional testing and possible etiology on the LA-CRF or an appropriate document.

Study Treatment Discontinuation

In the absence of an explanation for increased liver aminotransferases (ALT or AST) tests, such as viral hepatitis, preexisting or acute liver disease, or exposure to other agents associated with liver injury, the subject may be discontinued from study treatment. The investigator may determine that it is not in the subject’s best interest to continue study treatment. Study treatment must be discontinued and event reported as an SAE if:

- ALT or AST $> 8 \times$ ULN;
- ALT or AST $> 5 \times$ ULN for more than 2 weeks;
- ALT or AST $> 3 \times$ ULN and TBL $> 2 \times$ ULN or INR $> 1.5 \times$ ULN, and INR ;
- ALT or AST $> 3 \times$ ULN with the appearance of fatigue, nausea, vomiting, right upper quadrant pain or tenderness, fever, rash and/or eosinophilia ($> 5\%$ increase above baseline).

Subjects who develop a signal for liver injury will be monitored every 2 to 4 weeks if the study drug is discontinued. If the subject remains on study drug, they will be closely monitored for liver biochemistry results.

Subjects with a signal of elevated ($> 3 \times$ ULN) transaminases will have pharmacokinetic samples drawn in addition to repeat blood draws for liver biochemistry monitoring. These samples can be held for potential analysis based on the subject’s clinical outcome.

In addition, if close monitoring for a subject with moderate or severe hepatic laboratory tests is not possible, study treatment should be discontinued.

***Hy's Law Definition:** Drug-induced jaundice caused by hepatocellular injury, without a significant obstructive component, has a high rate of bad outcomes, from 10 to 50% mortality (or transplant).

The 2 "requirements" for Hy's Law are:

1. Evidence that a drug can cause hepatocellular-type injury, generally shown by an increase in transaminase elevations higher $3 \times \text{ULN}$ ($2 \times \text{ULN}$ elevations are too common in treated and untreated patients to be discriminating).
2. Cases of increased bilirubin (at least $2 \times \text{ULN}$) in people with concurrent transaminase elevations to at least $3 \times \text{ULN}$ (but it is almost invariably higher) and no evidence of intra- or extra-hepatic bilirubin obstruction (elevated ALP) or Gilbert's syndrome [Temple, 2006].

FDA Guidance for Industry titled "Drug-induced Liver Injury: Premarketing Clinical Evaluation" issued by the FDA on July 2009:

FDA Guidance for Industry:

1. The drug causes hepatocellular injury, generally shown by a higher incidence of 3-fold or greater elevations above the ULN of ALT or AST than the (nonhepatotoxic) control drug or placebo.
2. Among trial subjects showing such AT elevations, often with ATs much greater than $3 \times \text{ULN}$, one or more also show elevation of serum TBL to $> 2 \times \text{ULN}$, without initial findings of cholestasis (elevated serum ALP).
3. No other reason can be found to explain the combination of increased AT and TBL, such as viral hepatitis A, B, or C; preexisting or acute liver disease; or another drug capable of causing the observed injury.

References

Temple R. Hy's law: Predicting Serious Hepatotoxicity. *Pharmacoepidemiol Drug Saf.* 2006 April;15(Suppl 4):241-3.

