- h. At day 1 (visit 2) thru week 48 (visit 14), excluding visit 2b, a symptom directed physical exam will be conducted which includes weight and waist circumference.
- i. Includes biochemistry, coagulation and hematology panel. Visit 2b will only include liver biochemistry and INR testing.
- j. Includes oral/tympanic temperature, sitting blood pressure and pulse rate (sitting).
- k. The subject should rest in supine position for at least 10 minutes prior to the ECG.
- l. Only in the event the subject does not have a normal/negative or no clinically significant findings Pap test (or equivalent cervical cytology) from previous 12 months on record.
- m. TVU will be performed at screening and at week 52/EOT and in case of uterine bleeding during treatment.
- n. Endometrial biopsy will be performed at screening and in case of uterine bleeding during treatment. Subject may schedule the endometrial biopsy on a separate day, within the screening period. Subjects that require a retest biopsy due to insufficient or unevaluable result, will have an extended screening period and will be allowed an additional 15 days of screening (i.e., days -50 to -1). Screening biopsy results are valid for study entry up to 3 months from date of procedures for applicable subjects. Subjects who screen failed due to the COVID-19 pandemic study suspension and have a documented evaluable endometrial biopsy from the original screening period do not have to undergo a repeat biopsy should they decide to rescreen.
- o. Endometrial biopsy will be required at EOT or ED. For EOT/ED week 52 (visit 15) biopsies that are evaluated as insufficient material or unevaluable, a retest biopsy will be required. Any of the three pathologists can determine if a EOT/ED biopsy is insufficient or unevaluable. However, if two pathologists read the EOT/ED endometrial biopsy as evaluable and issue the same diagnosis, and the 3rd pathologist reads the biopsy as insufficient or unevaluable, the biopsy does not need to be repeated.

Footnotes continued on next page

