6 DISCONTINUATION

6.1 Discontinuation of Individual Subject(s) From Study Treatment

A discontinuation from treatment is a subject who enrolled in the study and for whom study treatment is permanently discontinued for any reason. The reason for discontinuation from study treatment must be documented in the subject's medical records.

A subject **must** discontinue study treatment for any of the following reasons:

- Withdrawal of informed consent
- Lost to follow-up
- If, for safety reasons, it is in the best interest of the subject that she be withdrawn, in the investigator's opinion
- Development of a medical condition that requires concomitant treatment with a prohibited therapy
- Development of seizures or other convulsive disorders
- Breaking of the randomization code during administration of the study drug by the investigator or by a member of the site staff. If the code is broken by the sponsor for safety reporting purposes or early time point analysis, the subject may remain in the study.
- Confirmed (within 72 hours from the notification of test result) decrease in platelets below 75,000 mm³, which does not normalize after 7 days or immediate withdrawal in case of platelets below 50,000 mm³.
- Development of severe hepatic abnormality defined as ALT or AST > 8 × ULN
- Confirmed (within 72 hours from the notification of test result) severe hepatic abnormality for any of the following:
 - ALT or AST > 5 × ULN for more than 2 weeks;
 - ALT or AST > 3 × ULN **AND** TBL > 2 × ULN or INR > 1.5 × ULN, and INR > 1.5; or

- ALT or AST $> 3 \times$ ULN with the appearance of fatigue, nausea, vomiting, right upper quadrant pain or tenderness, fever, rash and/or eosinophilia ($> 5\%$ increase from baseline).
- The subject becomes pregnant.
- Category 2 results of secondary or tertiary screening endometrial biopsy diagnosis.

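### The minimum 72-hour liver retest in Protocol Appendix 12.5 does not require INR or a differential count, so confirmation of two routes to mandatory discontinuation in Section 6.1 is permitted but not assured

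*Protocol*

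**What the plan says.** **The required retest.** Under Protocol Appendix 12.5, once aminotransferases exceed 3 × ULN or bilirubin exceeds 2 × ULN, the subject "should undergo detailed testing for liver enzymes (including at least ALT, AST, ALP and TBL). Testing should be repeated within 72 hours", counted from when the site is told of the result. INR comes later in the appendix, in a list for which, depending on the subject's history, "other testing may be appropriate including" the item "Other laboratory tests including INR and DBL". No retest text mentions a blood count. The appendix describes the repeat draws for raised transaminases as liver biochemistry. In the table of Section 5.4.3, INR sits in the coagulation panel and eosinophils in hematology; neither is under liver biochemistry.

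**The stopping rule.** Section 6.1 makes discontinuation mandatory for "Confirmed (within 72 hours from the notification of test result) severe hepatic abnormality for any of the following", and the synopsis has the same structure. The three criteria are:

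- ALT or AST above 5 × ULN for more than 2 weeks;
- ALT or AST above 3 × ULN with a bilirubin or INR condition;
- ALT or AST above 3 × ULN with one of several features, ending in "right upper quadrant pain or tenderness, fever, rash and/or eosinophilia".

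**The second list.** The discontinuation part of Appendix 12.5 gives the same criteria and requires both stopping and SAE reporting. It does not say that the finding must be confirmed.

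**Routine sampling.** Under Table 1, footnote i, laboratory visits include coagulation and hematology, with one exception: "Visit 2b will only include liver biochemistry and INR testing". Section 5.4.3 allows unscheduled and repeat tests where clinically indicated.

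**The concern.** When a rule compels an action only after confirmation, the test that confirms it should be as mandatory as the rule. Here a site can follow the stated minimum exactly and hold a complete retest with no INR and no eosinophil count.

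Scheduled visits do not fill the gap. From Week 4 they are 28 days apart, against a 72-hour clock. At Week 2 (Visit 2b) INR is drawn but eosinophils are not, even at the first sample. The next scheduled count is at Week 4, which is Day 29 − Day 15 = 14 days later.

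Section 1.5 of the Protocol classes liver injury as an important potential risk, long-term safety is a primary objective, and Section 2.2.2 notes that 45 mg once daily had not been studied before. Meeting a withdrawal criterion also has consequences beyond the individual decision. Under Section 10.2 the Liver Safety Monitoring Committee reviews cases that meet those criteria, and under Section 5.8.2 a discontinuation for raised liver enzymes is an SAE. A case that qualifies only through INR or only through eosinophilia could be handled differently by two sites that both comply with the text.

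**Working it through.** The documents give no figure to reproduce, so the check compares the retest panel with the stopping criteria, route by route. A route is one combination of findings that satisfies a criterion. Required inputs are ALT, AST, ALP and total bilirubin (12.5), plus the enquiry about hepatobiliary symptoms that 12.5 also calls for. The second criterion is first read as in the synopsis and the 12.5 definition: raised ALT or AST, together with either bilirubin or INR.

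| Criterion needing confirmation | Routes | Covered by the minimum | Not covered |
|---|---|---|---|
| ALT/AST > 5 × ULN for more than 2 weeks | 1 | 1 (needs serial values, but no other analyte) | 0 |
| ALT/AST > 3 × ULN with bilirubin or INR | 2 | 1 (bilirubin) | 1 (INR only) |
| ALT/AST > 3 × ULN with a named feature | 7 | 6 (fatigue, nausea, vomiting, right upper quadrant pain or tenderness, fever, rash) | 1 (eosinophilia only) |
| Total | 1 + 2 + 7 = 10 | 1 + 1 + 6 = 8 | 10 − 8 = 2 |

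**Effect of the INR wording.** The criterion differs from place to place:

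- The synopsis and the 12.5 definition use an absolute INR above 1.5 as an alternative to bilirubin.
- Section 6.1 gives INR as a multiple of ULN as that alternative, then adds a further absolute INR condition joined by a comma and a conjunction.
- The 12.5 discontinuation list gives the multiple of ULN and then breaks off. This may be an artefact of reading the PDF and is not counted as an error here.

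Taken literally, Section 6.1 needs INR for the whole second criterion. Coverage then falls to 1 + 0 + 6 = 7 of 10 routes, and even a confirmed bilirubin rise would need an INR result.

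**Is confirmation required at all?** Section 6.1 and the synopsis say yes for these three criteria. The 12.5 discontinuation list does not. The definitions in 12.5 add to the doubt: they introduce the moderate and severe classes as confirmed abnormalities, then give further severe criteria without repeating the condition. On the list, a first-draw INR could compel stopping and SAE reporting; on Section 6.1, it could not until confirmed.

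**The case against.** The case on the other side is substantial, and most of it stands.

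- A reader might infer that 12.5 limits the retest to four analytes. It does not: the panel is a floor, and a site may add INR or a blood count.
- A reader might infer that the INR and eosinophilia routes cannot be confirmed. Section 5.4.3 permits repeat tests, 12.5 asks that confirmed abnormalities be thoroughly characterized, and a requirement to confirm a raised INR naturally suggests repeating it. What remains is that the repeat is optional while the rule is mandatory.
- A reader might infer that a woman with an unconfirmed INR would stay on drug and go unreported. The 12.5 list could already compel stopping and SAE reporting on the first value. Investigators may also withdraw subjects for safety or class other results as severe, and 12.5 calls for stopping where close monitoring is not possible. The defect is that the two lists give different answers.
- The primary liver tables are barely touched. SAP Section 6.5.2.1 uses each subject's highest value, asks for no confirmation and has no INR or eosinophil category. The aminotransferase rise would be counted; the extra feature would not appear there. SAP Section 2.2 also describes the liver panel as monitoring liver test elevations in general.
- A reader might size the problem as 580 × 9/352 = 14.8 women per arm retested. The documents do not support that figure. Section 2.2.2 reports that 7 of the 9 phase 2b cases received 120 mg/day or more and that modelling predicted no elevations above 3 × ULN at 30 or 45 mg once daily. Section 1.5 reports none observed at 30 mg once daily.

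**Conclusion.** The gap is real but narrow. Two of ten confirmation routes, INR-only and eosinophilia-only, depend on analytes that the minimum retest does not require; the bilirubin and symptom routes are covered. If Section 6.1 is taken literally on INR, the uncovered routes rise to three. Two contradictions go with it: whether confirmation is needed, and how the INR criterion is worded.

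This rests on one inference: that the 12.5 retest is the confirmation meant in Section 6.1. The shared 72-hour clock and the reference in 12.5 to confirmed abnormalities support it, but neither section says so.

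The number of women affected should be small. It cannot be derived, because the documents give neither a reliable rate above 3 × ULN at these doses nor the share whose only additional feature is INR or eosinophils. The point is a cheap improvement to a safety rule and does not undermine the planned liver analysis.

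**What to change.** Reconcile Protocol Appendix 12.5 with Section 6.1 and the synopsis on three matters:

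1. Either the required 72-hour retest reports every analyte that a mandatory criterion uses, or the protocol states how a criterion is judged when its analyte was not retested. The same check applies to a signal first seen at Visit 2b, where no eosinophil count is drawn.
2. All lists state consistently whether confirmation is required before discontinuation and SAE reporting.
3. The INR criterion has one wording throughout.

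Thresholds and clinical action remain with the sponsor's liver experts; no view is offered here on which version is right. The cost is protocol wording and, at most, additional tubes for tests already in the study's laboratory panels, taken at a blood draw that is already required, for a few women.

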Medications taken after the first dose of study medication and through the last study-related activity will be documented on the appropriate CRF as concomitant medication. Prior and concomitant medications to be documented include but are not limited to: vitamins, herbal remedies (e.g., St. John's wort, valerian), over the counter and prescription medications.

Subjects will be instructed not to take any concomitant medication without first consulting the investigator or study coordinator throughout the duration of the study.

Prohibited Concomitant Medications:

The following medications and therapies are prohibited throughout the study (from signing of informed consent form [ICF] through the last study-related activity):

- Use of hormonal medications such as hormone therapy, HRT or hormonal contraception or any treatment for menopausal symptoms (prescription, over the counter or herbal).
- Investigational research products that have not been approved for any indication in the country where the subject is enrolled.
- Strong or moderate CYP1A2 inhibitors are prohibited.

Duration of Treatment:

Subject will take study drug daily from day 1 (randomization) for a duration of 52 weeks.

Formal Stopping Rules

Subject Discontinuation:

A subject **must** be withdrawn from the study treatment for any of the following reasons:

- Withdrawal of informed consent.
- Lost to follow-up.
- If for safety reasons it is in the best interest of the subject that she be withdrawn, in the investigator's opinion.
- Development of a medical condition that requires concomitant treatment with a prohibited therapy.
- Development of seizures or other convulsive disorders.
- Breaking of the randomization code during administration of the study drug by the investigator or by a member of the site staff. If the code is broken by the sponsor for safety reporting purposes or early time point analysis, the subject may remain in the study.
- Confirmed (within 72 hours from the notification of test result) decrease in platelets below 75,000 mm³, which does not normalize after 7 days or immediate withdrawal in case of platelets below 50,000 mm³.
- Development of severe hepatic abnormality defines as ALT or AST > 8 × ULN.
- Confirmed (within 72 hours from the notification of test result) severe hepatic abnormality defined as any of the following:
 - ALT or AST > 5 × ULN for more than 2 weeks;
 - ALT or AST > 3 × ULN **AND** TBL > 2 × ULN or INR > 1.5; or

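### The mandatory liver stopping rules differ between Section 6.1, the synopsis and Appendix 12.5: on 72-hour confirmation for two criteria, and on the INR threshold

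*Protocol*

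**What the plan says.** Three places in the protocol state when study drug must be stopped for liver findings.

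- **Section 6.1.** One bullet has no condition: "Development of severe hepatic abnormality defined as ALT or AST > 8 × ULN". The next opens with "Confirmed (within 72 hours from the notification of test result) severe hepatic abnormality for any of the following" and covers three criteria: ALT or AST above 5 × ULN for more than 2 weeks; above 3 × ULN with raised bilirubin (TBL) or INR; and above 3 × ULN with listed symptoms or eosinophilia. The bilirubin/INR limb reads "TBL > 2 × ULN or INR > 1.5 × ULN, and INR > 1.5".
- **Synopsis, Formal Stopping Rules.** The structure is the same: above 8 × ULN stands alone, and the other three fall under "Confirmed (within 72 hours from the notification of test result) severe hepatic abnormality defined as any of the following". The bilirubin/INR limb is simpler: "TBL > 2 × ULN or INR > 1.5; or".
- **Appendix 12.5, Study Treatment Discontinuation.** All four criteria appear under "Study treatment must be discontinued and event reported as an SAE if". Neither the lead-in nor any item mentions confirmation.

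Earlier in Appendix 12.5, a retest is ordered within 72 hours of notification for aminotransferases above 3 × ULN or bilirubin above 2 × ULN, and confirmed abnormalities are graded moderate or severe in a small table. A separate list of further severe abnormalities follows, with an INR limit of 1.5. The INR text in the 12.5 stop list itself breaks off in the available copy and is not relied on here.

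**The concern.** A site that follows the Appendix 12.5 list literally stops drug and files an SAE on the first qualifying result. A site that follows Section 6.1 waits for the retest and need not stop if the result is not reproduced. The INR limb adds a second way for the same result to give two answers.

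Several things depend on which text is applied. A stop under Section 6.1 applies to a subject "for whom study treatment is permanently discontinued for any reason", so there is no trial-level route back. Sections 5.8.1.2 and 5.8.2 make a liver-related discontinuation an important medical event and an SAE. The liver committee in Section 10.2 receives cases because they meet the withdrawal criteria. Under Section 8.3, a woman who met a withdrawal criterion and stayed on drug is a PD2 deviation. Liver injury is named an important potential risk in Section 1.5, so this rule should work the same way at all of the roughly 250 planned centers.

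**Working it through.** The plan gives no figure to reproduce. The check is a comparison of texts, plus one threshold calculation.

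**Step 1: confirmation wording, criterion by criterion.**

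| Criterion (ALT or AST) | Synopsis | Section 6.1 | 12.5 stop list |
|---|---|---|---|
| > 8 × ULN | no condition | no condition | no condition |
| > 5 × ULN for more than 2 weeks | confirmed | confirmed | no confirmation |
| > 3 × ULN with TBL > 2 × ULN or raised INR | confirmed | confirmed | no confirmation |
| > 3 × ULN with symptoms or eosinophilia | confirmed | confirmed | no confirmation |

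- Criteria whose wording differs: 4 − 1 = 3.
- Of these, the 2-week criterion needs serial values by its own terms, so the missing word changes nothing: 3 − 1 = 2 criteria where one unreproduced result can change the action.

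**Step 2: follow one case.** Suppose a woman's first sample shows ALT above 3 × ULN with bilirubin above 2 × ULN, and the retest shows neither.

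- Under the 12.5 list read literally, she is stopped and an SAE is filed on the first result. If she is still on drug when the retest comes back, she can be counted as PD2.
- Under Section 6.1, the criterion was never confirmed. There is no mandatory stop, no SAE through the discontinuation route, no PD2, and no referral to the committee on that criterion.

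**Step 3: the INR limb.** The synopsis and the 12.5 definition of severe abnormality use INR > 1.5. I read the two INR conditions in Section 6.1 as joined to each other, so its effective threshold is the larger of 1.5 × ULN and 1.5. The laboratory ULN for INR is not in the documents, so it is assumed over a range:

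| Assumed ULN | 1.5 × ULN | Section 6.1 threshold | INR of 1.6 under synopsis and 12.5 definition | INR of 1.6 under 6.1 |
|---|---|---|---|---|
| 1.0 | 1.50 | 1.50 | met | met |
| 1.1 | 1.65 | 1.65 | met | not met |
| 1.2 | 1.80 | 1.80 | met | not met |

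The thresholds coincide for a ULN of 1.0 or lower. Section 6.1 is harder to meet for any ULN above 1.0.

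**Step 4: what reaches the analysis.** The liver categories in SAP 6.5.2.1 use each woman's highest value on treatment, and the stopping rule plays no part in their definition. The classification does enter the counts of serious TEAEs and of TEAEs leading to discontinuation (SAP 6.5.1) and the PD2 summary (SAP 6.2.2).

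**The case against.** The best defence is that an appendix silent on timing does not contradict a section that states it. Section 6.1 is the titled discontinuation section, the SAE definition in Section 5.8.2 refers to it, and the synopsis agrees with it. Appendix 12.5 orders the same 72-hour retest and speaks of confirmed abnormalities, so its list may simply restate the criteria and add SAE reporting. That is probably the intent, and a careful site could read it so. It is still an inference: the list is worded as an order, and no precedence rule was found. Section 5.8.1.2 sends sites to 12.5 for detailed liver instructions, and Section 1.5 mentions stopping rules and liver assessment with a pointer to 12.5. Nor does this reading resolve the INR difference.

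On INR, the double condition in Section 6.1 may be editing residue, and it has no effect at a ULN of 1.0 or below. Both points are fair, but the sentence is complete as it stands and a site would have to apply it.

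The safety consequences are limited, and this stands. The literal 12.5 reading is the cautious one. Section 6.1 lets the investigator withdraw a woman earlier: "If, for safety reasons, it is in the best interest of the subject that she be withdrawn". Appendix 12.5 gives similar discretion, has the central laboratory send alerts, and requires immediate notice to the sponsor of severe abnormalities possibly attributable to drug. SAP 2.2 has a liver panel monitoring elevations throughout, so oversight does not rest on withdrawal cases alone.

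A reader might also infer that 12.5 makes ALT or AST above 8 × ULN wait for a retest, because it grades confirmed abnormalities. The documents do not support that. The word introduces the moderate/severe table. The list headed by above 8 × ULN opens separately, without it, and all three stopping lists leave that criterion unconditional.

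**Conclusion.** The inconsistency is real and small. Confirmation is missing from the 12.5 list for three of four criteria, and this can change the action for two. The INR threshold differs between Section 6.1 and both the synopsis and the 12.5 severity definition whenever the laboratory ULN exceeds 1.0. The effect is on uniform site action and on classification as mandatory stop, SAE, liver-committee case or PD2.

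Few women are likely to be affected. To be affected, a woman must meet one of the two criteria on a result that is then not reproduced, or have an INR between the two thresholds. The documents give no rate for either, so the number cannot be estimated. A reader might try to size it from the phase 2b transaminase elevations, but those count women above a multiple of ULN, which is a different event.

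The conclusion assumes that sites apply the text as written, and that the two INR conditions in Section 6.1 qualify each other and not the bilirubin limb. This merits a correction. It does not call the safety analysis into question.

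**What to change.** Replace the stop list in Appendix 12.5 with a cross-reference to Section 6.1: above 8 × ULN stops treatment on the first value, and the other three criteria stop it when confirmed within 72 hours of notification. Keep the statement that the investigator may stop earlier for safety. Set the INR limit to > 1.5 in Section 6.1 and throughout Appendix 12.5, as the synopsis and the 12.5 severity definition already have it. Copying Section 6.1 unchanged would not be enough, because it would carry the double INR condition into the appendix.

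The cost is protocol wording. The 72-hour retest is already ordered, so no tests or patients are added and the SAP needs no change.
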